Study Protocol with Statistical Analysis Plan

Prospective Randomized Study of the modulating effect of MEXIDOL® as an adjuvant stimulant of the cognitive-emotional component of the rehabilitation treatment in patients with acute cerebral failure

NCT Number: NCT06221826

Pharmasoft
April 10, 2023

Study Protocol

The study procedures for the visits are presented in Table 1.

Conditions	Acute Cerebral Failure (Ischemic Stroke, Traumatic Brain Injury)
Study Design	Study Type: Interventional Primary Purpose: Treatment Study Phase: Phase 4 Interventional Study Model: Parallel Assignment Number of Arms: 2 Masking: None (Open Label) Allocation: Randomized (1:1) Enrollment: 60 [Actual] Time Frame: 66 days (I: parenteral therapy 10 days; II: oral therapy 8 weeks)
Arms	Mexidol and Standard Therapy Standard Therapy
Method of Application	Mexidol, solution for intravenous (IV) and intramuscular administration, IV 500 mg for 10 days, then Mexidol FORTE 250, film-coated tablets 250 mg, orally 1 tablet 3 times a day for 8 weeks.
Standard and Concomitant therapy	Standard treatment: basic practices of kinesitherapy, occupational therapy, speech therapy, clinical psychology, supplemented by adjuvant procedures of electrotherapy and rehabilitation environment therapy. The patient's rehabilitation load was at least 3 hours a day for 12 days. Patients may continue their pre-study therapy for other chronic conditions if, in the opinion of the investigator, they do not interfere with the results of this study and are administered at a stable dose during the study.
Primary Purpose	To evaluate the effect of pharmacological modulation of the rehabilitation process with the drug Mexidol as an adjuvant component of rehabilitation treatment of emotional and cognitive disorders in patients with Acute Cerebral Failure (Ischemic Stroke, Traumatic Brain Injury).
Secondary Purpose	To establish the possibility of identifying an individual clinical response to Mexidol therapy (responders and non-responders) and to determine indications for including the drug in an individual rehabilitation program.
Exploratory Purpose	 To establish, using neurophysiological methods, the effect of the drug on perfusion-metabolic coupling (TCDG-EEG [transcranial dopplerography and electroencephalography] monitoring at the time of drug infusion) as an indirect indicator of increased metabolic activity of the brain. To establish, using clinical scales, the presence of a connection between the use of the drug Mexidol and the dynamics of recovery of the emotional-cognitive status of patients with acute cerebral insufficiency, during the period of permanent inpatient-outpatient rehabilitation treatment.
Research objectives (Outcome Measures)	1. Assessment of attentiveness and performance – the presence of the effect of Mexidol infusion on the change in the results of the Schulte test [work efficiency] before the start of the course, at the end of the

	course of infusion therapy and after the course of therapy with the			
	tablet form of Mexidol FORTE 250			
	Dynamics of cognitive status according to the Montreal Cognitive			
	Assessment (MoCA test)			
	3. Severity of depression according to the Beck Depression Inventory			
	(BDI scale)			
	4. Reduction in anxiety according to the Hospital Anxiety and			
	Depression Scale (HADS)			
	5. The degree of severity and dynamics of the Post Intensive Care			
	Syndrome (PICS) according to the PICS-score			
	6. Dynamics of level of mobility according to the Rivermead index			
	7. Dynamics of the level of life according to the Rehabilitation Routing			
	Scale (RRS)			
	8. Severity and dynamics of muscle strength according to the Muscle			
	Strength Quantitative Rating (MRC) Scale			
	9. Variants of specific dynamics of neurophysiological parameters of			
	perfusion (transcranial dopplerography) and metabolism			
	(electroencephalography) at the time of infusion of Mexidol (event			
	related monitoring)			
Safety and Tolerability	Incidence of Treatment-Emergent Adverse events related to Mexidol			
Criteria:	S			
Inclusion Criteria:	• ≥18 years old			
inclusion Criteria.	Signed Informed Consent Form			
	Acute Cerebral Failure (Ischemic Stroke, Traumatic Brain Injury)			
	 Montreal Cognitive Assessment (MoCA test) >15; ≤22 			
Evaluaion Cuitonio				
Exclusion Criteria:	• < 18 years old			
	• Epilepsy			
	• Pregnancy			
	Acute failure of one or more organ systems			
	 Purulent-inflammatory disease of any localization Participating in any other clinical trial 			
Ethical and Lagal Aspects	This study will be conducted with the highest respect for the individual			
Ethical and Legal Aspects				
	participants in accordance with the requirements of this study protocol			
	and also in accordance with the following:The ethical principles that have their origin in the Declaration of			
	Helsinki.			
	International Conference on Harmonisation E6 Good Clinical			
	Practice: Consolidated Guideline.			
	All applicable laws and regulations, including, without limitation, privacy laws, clinical trial disclosure laws, and regulations.			
	privacy laws, clinical trial disclosure laws, and regulations.			

Table 1. Schedule of study procedures.

	Visit				
	Screening				
The study procedures		Visit 2 Day 1	Visit 3 Day 10	Video visit 4 Day 38	Visit 5 Day 66
Obtaining Informed Consent					
Checking inclusion/exclusion criteria		X			
Collection of anamnesis data					
Conducting a physical examination		X			
Measurement of BMI	X				
Body temperature	X				
Vital signs of the body's condition (mean BP, HR, RR)	X	X	X		X
Randomization		X			
The Rehabilitation Routing Scale (RRS)	X X		X	X	X
The Montreal Cognitive Assessment (MoCA test)			X		X
The Beck Depression Inventory (BDI scale)		X	X	X	X
The Hospital Anxiety and Depression Scale (HADS)		X	X	X	X
The Rivermead index		X	X	X	X
The Muscle Strength Quantitative Rating Scale (MRC)		X	X	X	X
The Post Intensive Care Syndrome (PICS) score		X	X	X	X
The Schulte test		X	X		X
Neurophysiological parameters (EEG, TCDG)		X			
Administration of the study drug intravenously		X	XX		
Dispensation of the study drug for oral administration			X		
Return of the drug and assessment of treatment compliance (if the drug is taken orally)					X
Question about the intake of concomitant drugs		X	X	X	X
Monitoring of adverse events		X	X	X	X

Statistical Analysis Plan

To create conditions for an independent assessment of the obtained results, statistical data processing at the end of the study will be performed by employees not involved in the management of patients participating in the study. Data processing will be performed in the software environment of the TIBCO® StatisticaTM v.13 and R v.4.4.1 and higher packages or similar, corresponding to the tasks of statistical analysis.

For statistical analysis of quantitative features, compliance with the normal distribution law will be preliminarily assessed by one of the generally accepted methods (Shapiro-Wilk criterion). When testing statistical hypotheses for indicators with a normal distribution, parametric criteria will be used, and for indicators whose distribution differs from normal, nonparametric criteria will be used.

The following indicators will be calculated as descriptive statistics parameters for continuous (quantitative) data:

- n number of valid observations;
- M, Mean arithmetic mean;
- Me, Median median;
- Min minimum value;
- Max maximum value;
- Q1 lower quartile;
- Q3 upper quartile;
- Range range;
- IQR interquartile range;
- SD standard deviation;
- SE standard error of the mean;
- w Wilcoxon-Mann-Whitney test for independent groups;
- t Student's t-test with Welch's correction for independent groups;
- f Fisher's exact test;
- $\gamma 2$ Chi-square test.

For ordinal, categorical and qualitative variables:

- absolute frequency (number of observations);
- relative frequency (expressed as a percentage).

The results of the assessment of quantitative variables, the distribution of which corresponds to the law of normal distribution, will be presented as M±SD, where M is the mean value, and SD is the standard deviation. The results of the assessment of quantitative variables, the distribution of which does not correspond to the law of normal distribution, will be presented as Me [Q1; Q3], where Me is the median, and Q1 and Q3 are the lower and upper quartiles.

Efficacy and safety indicators, as well as their changes, will be presented using descriptive statistics by visits and therapeutic groups. For study visits, qualitative (dichotomous) indicators will be compared between groups based on the Pearson $\chi 2$ criterion, the Pearson $\chi 2$ criterion with Welch's correction, or the Fisher exact test for tables of arbitrary dimension (if the frequency of the indicator in at least one of the subgroups is 5 or less).

Comparison of groups by quantitative indicators can be carried out using the Student's T-test and the Mann-Whitney test. Comparison of intra-group parameters before and after treatment can be

performed using the T-test for related samples or the Wilcoxon-Mann-Whitney test. Statistically significant values are p-level <0.05.

Safety analysis will be performed for the safety population. The following safety parameters are provided for in this study:

- Total number of AEs, stratified by severity and frequency;
- Frequency of AEs, related, in the opinion of the physician-investigator, to the use of the study drug;
- Frequency of serious adverse events (SAEs), related, in the opinion of the physician-investigator, to the use of the study drug;
 - Proportion of patients with at least one AE;
 - Proportion of patients with 2 or more AEs.

The dynamics of quantitative safety parameters relative to baseline values will be assessed and compared with each other using ANOVA with repeated measures. This method allows to simultaneously check for statistically significant dynamics (at least one average value at one time point differs from the others), and also to compare the dynamics and ranges of the indicator values when obtaining the compared drugs. In case of inappropriateness of the use of parametric methods, a similar analysis of the change in the distribution of indicators during therapy will be carried out using non-parametric analogues - the Friedman criterion and the Wilcoxon signed rank criterion, and intergroup comparisons of changes - using the Wilcoxon-Mann-Whitney criterion.

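### Outcome 1 labels the Schulte result after the tablet course as an effect of the Mexidol infusion, but at Day 66 the two-arm design supports a claim only for the whole infusion-then-tablets sequence

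*Combined protocol and SAP*

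**What the plan says.** Item 1 of Research objectives (Outcome Measures) concerns "the presence of the effect of Mexidol infusion on the change in the results of the Schulte test". It lists three assessments under that one effect: a baseline, the end of infusion, and the end of oral treatment. The last two are given as the end of the "course of infusion therapy and after the course of therapy with the" "tablet form of Mexidol FORTE 250".

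The Study Design row gives "Number of Arms: 2", parallel, randomized 1:1 and open label. The Arms row reads "Mexidol and Standard Therapy Standard Therapy", that is, Mexidol added to standard therapy against standard therapy. Method of Application sets the Mexidol regimen as "IV 500 mg for 10 days, then Mexidol FORTE 250, film-coated tablets 250 mg, orally 1 tablet 3 times a day for 8 weeks".

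Table 1 shows a single randomization at Day 1, the Schulte test at Days 1, 10 and 66, and tablet dispensing at Day 10.

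The Statistical Analysis Plan presents efficacy indicators and their changes by visit and treatment group. It allows a t-test or Mann-Whitney test between groups, and paired tests within groups. It does not say which visit or contrast represents the infusion effect.

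**The concern.** Item 1 names a single cause, the infusion, for a result that is also measured after eight weeks of a different formulation. A team that follows this definition would report a Day 66 difference as an infusion effect, although tablets taken after Day 10 could have produced some or all of it.

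This matters because the Schulte test heads the outcome list and because the Secondary Purpose seeks indications for including the drug in individual rehabilitation programs. Readers with that aim would want to know whether a benefit belongs to the infusion or to the course as a whole.

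**Working it through.** **Inputs.** Infusion phase, 10 days; oral phase, 8 weeks; total time frame, 66 days (Study Design and Method of Application). Two arms (Study Design, Arms). Schulte test at Days 1, 10 and 66; tablets dispensed at Day 10 (Table 1).

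**Step 1: the plan's own figure.** 8 × 7 = 56 days of tablets, and 10 + 56 = 66 days. This reproduces the stated time frame exactly. The planned phases therefore follow one another with no gap, and tablets are expected to start after Day 10.

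**Step 2: what each between-arm contrast measures.** Define, for the Mexidol arm relative to standard therapy:

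- I = the effect present at the end of the infusion phase;
- c = the share of I that would still be present at Day 66 without tablets;
- T = what the tablets add by Day 66 in patients who have had the infusion.

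Then:

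- Day 10 contrast = I, provided the test is done before the first tablet;
- Day 66 contrast = c × I + T.

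The infusion's part of the Day 66 contrast is c × I. Recovering it needs c or T, and estimating either would take a group assigned to stop after the infusion. The design has none.

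**Step 3: illustration.** The documents give no effect size or standard deviation for the Schulte test, so the values below are assumed, in SD units, purely to show the ambiguity.

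| I | c | T | Day 10 contrast | Day 66 contrast | Infusion part at Day 66 (c × I) |
|---|---|---|---|---|---|
| 0 | 0 | 0.5 | 0 | 0 + 0.5 = 0.5 | 0 |
| 0.5 | 1 | 0 | 0.5 | 0.5 + 0 = 0.5 | 0.5 |
| 0.5 | 0.5 | 0.25 | 0.5 | 0.25 + 0.25 = 0.5 | 0.25 |

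All three cases give the same Day 66 difference, while the infusion's share of it ranges from none to all. In the first case the infusion has no effect, yet item 1's wording would credit it with 0.5. The second and third cases agree at both Day 10 and Day 66 and still differ in the infusion's share, so adding the Day 10 result does not resolve the matter.

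**Step 4: does the SAP settle the label?** Results by visit and arm will contain both the Day 10 and the Day 66 comparisons, but neither is tied to a named effect. The optional within-arm tests do not help, because both arms receive rehabilitation and a before-after change in the Mexidol arm includes that recovery. Item 1 is left as the only text that says what the Schulte result means.

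**The case against.** The best reply is that this is one loose phrase. Item 1 itself mentions the tablet course. The Primary Purpose speaks of the drug and the Secondary Purpose of the therapy, and the arms compare Mexidol as a whole with standard therapy. The SAP plans no infusion-specific test at Day 66, and its output by visit and arm already contains the two comparisons that are needed.

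Much of that stands. The planned comparisons are usable and the Day 66 comparison fits the Primary Purpose. It does not rescue the label: item 1 says infusion, not drug or therapy, and an outcome definition governs what may later be claimed from it.

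Four stronger readings are tempting, and the documents do not support them:

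- A reader might infer that the Day 66 comparison is invalid. It is a randomized contrast and remains valid for the full sequence.
- A reader might infer that the plan also credits the Day 10 to Day 66 change to the tablets. No section makes that claim.
- A reader might infer that Day 10 isolates the drug effect of the infusion. It is free of tablets only. The trial is open label and describes no placebo infusion, so expectation effects remain. Table 1 also puts the Schulte test and tablet dispensing at one visit without giving their order.
- A reader might infer that every Mexidol patient in fact moved from infusion to tablets. The documents give the assigned regimen, not patient disposition. What can be said is that no arm is assigned one phase alone.

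**Conclusion.** The point holds as a fault of attribution in the definition of the first-listed outcome. It affects the meaning of one of the two post-baseline Schulte assessments, Day 66. It has no numerical size: no error rate, power figure or p-value changes, and the number of days spent on each formulation does not measure a bias.

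The conclusion rests on the regimen, arms and single randomization as written. The reading of Day 10 as an infusion-phase contrast further assumes that the test precedes the first tablet. The 10 + 56 = 66 arithmetic implies this, but Table 1 does not state it. The wording should be corrected before results are reported; the trial is not undermined.

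**What to change.** Split item 1 into two named between-arm contrasts:

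- **(a) Infusion phase.** Difference in Schulte results at Day 10, adjusted for the Day 1 value. State that the test is done before any tablet is taken, and that without a placebo infusion in this open-label trial the contrast includes expectation effects.
- **(b) Full Mexidol sequence.** Difference in Schulte results at Day 66, adjusted for the Day 1 value.

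Carry both labels into the SAP, and state there that Day 66 supports no claim about the infusion alone. Adjustment for Day 1 gives a definite form to the change that item 1 refers to and uses a value already collected. The SAP currently names only unadjusted two-group tests for efficacy, so it needs a line specifying the adjusted model.

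The cost is wording and a little analysis, with no new visits or data. The sponsor gives up an infusion-specific claim at Day 66, which the design could not support in any case.

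### The SAP does not limit within-arm before/after tests to description, so improvement expected without any drug effect could be used to answer an efficacy outcome such as the Schulte test

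*Combined protocol and SAP*

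**What the plan says.** The trial is open label with two parallel arms: "Masking: None (Open Label) Allocation: Randomized (1:1) Enrollment: 60 [Actual" (protocol, Study Design).

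Outcome 1 (protocol, Research objectives) is "the presence of the effect of Mexidol infusion on the change in the results of the Schulte test [work efficiency", assessed before the course, at the end of the infusions and after the tablets. The comparator is not mentioned.

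The SAP paragraph on quantitative indicators has three relevant statements, in this order:

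- Between arms: "Comparison of groups by quantitative indicators can be carried out using the Student's T-test and the Mann-Whitney test".
- Within arms: "Comparison of intra-group parameters before and after treatment can be", continuing "performed using the T-test for related samples or the Wilcoxon-Mann-Whitney test".
- One threshold for both: "Statistically significant values are p-level <0.05".

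Just before this, the SAP says that efficacy and safety indicators and their changes will be summarised descriptively by visit and arm. A between-arm test of changes is named only in the SAP's safety analysis, as the non-parametric alternative to repeated-measures ANOVA. No primary test is named, and the two kinds of comparison are not ranked.

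**The concern.** A before/after test in one arm asks whether patients changed. It does not ask whether Mexidol changed them. Here, change is expected in both arms for reasons that the protocol itself sets out:

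- The condition is acute stroke or brain injury, followed for 66 days.
- Standard treatment includes a rehabilitation load of 3 hours or more daily over 12 days.
- The same instruments are repeated; Table 1 shows the Schulte test on Days 1, 10 and 66, so practice can contribute.

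For MoCA alone, selection may add regression to the mean, because entry requires "Montreal Cognitive Assessment (MoCA test) >15; ≤22" and MoCA is also outcome 2.

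Two misuses are open. A significant paired test in the Mexidol arm could be given as the answer to outcome 1. Or a result that is significant on Mexidol and not significant on standard therapy could be reported as a drug effect, although that pattern does not test the difference between arms. A SAP should settle in advance which comparison carries the conclusion; this one leaves it open.

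**Working it through.** **Stated figure.** There is none to reproduce. The documents give no power calculation, effect size or SD.

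**Inputs from the documents.** Total enrolment is 60 ("Enrollment: 60 [Actual") with 1:1 allocation, and the threshold is p<0.05.

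**Assumptions.** 30 per arm (60/2; arm sizes are not stated), two-sided tests (sidedness is not stated), normally distributed changes, zero drug effect, and the same standardised change d = mean change / SD of change in both arms. Since d is unknown, a range is shown.

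**Step 1: paired t-test in the Mexidol arm.** With n=30 there are 29 degrees of freedom and the noncentrality is d×√30. At d=0.3, for example, it is 0.3×5.477=1.643. The chance of significance is P(|T|>t(0.975; 29)) under the noncentral t distribution.

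**Step 2: discordant pattern.** Let u be the chance of a significant improvement in one arm. The arms are independent, so the chance of significant improvement on Mexidol but not on control is u×(1−u). This has its maximum of 0.25 at u=0.5, which is reached near d=0.36.

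| d | Mexidol-arm paired test significant | Significant improvement on Mexidol, not on control |
|---|---|---|
| 0 | 5.0% | 2.4% |
| 0.1 | 8.3% | 7.1% |
| 0.2 | 18.5% | 15.0% |
| 0.3 | 35.5% | 22.9% |
| 0.36 | 47.9% | 25.0% |
| 0.5 | 75.4% | 18.6% |
| 0.8 | 98.8% | 1.1% |

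The last column is calculated from unrounded values of u.

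**Step 3: between-arm test of change.** In 20,000 simulated trials at each of d=0, 0.3, 0.5 and 0.8, a Welch t-test on change was significant in 4.8% to 5.2%. The shared recovery cancels. A false result in favour of Mexidol therefore occurs in about 5%/2 = 2.5% of trials, whatever d is.

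**Step 4: regression to the mean on MoCA.** I simulated selection at scores 16 to 22, assuming a total SD of 4.5, a source-population mean of 17 to 24 and a reliability of 0.7 to 0.9. The mean shift ran from −0.5 to +1.2 points and gave a significant within-arm change in 5% to 52% of trials. The shift is about zero when the source mean is 19 and downward when it is 17. Neither its size nor its direction can be fixed from the documents.

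**The case against.** The strongest reply is that this is a randomised, parallel-group trial with planned between-arm tests for both quantitative and dichotomous indicators. In that setting, the effect of the infusion on a change can fairly be read as a difference in change between arms. Outcome 1 names no within-arm test, the intra-group sentence is only permissive, and the SAP's list of statistics labels both its t-test and its rank test as being for independent groups.

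Much of this stands. A reader might infer that the plan treats before/after improvement as proof of efficacy, or gives up the benefit of randomisation. The documents do not support that: the SAP never makes such a claim, and the randomised comparison is planned and available. What remains is an omission. The between-arm sentence is equally permissive, and nothing sets it above the within-arm one.

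A reader might also take a discordant-pattern rate of 19–25% as typical. That range comes from assuming d of 0.3 to 0.5, which brackets the mathematical maximum. Intensive rehabilitation could produce a larger d; at 0.8 both arms would nearly always be significant and the pattern would occur in 1% of trials, below the 2.5% of a between-arm test. But the Mexidol-arm p-value alone would then be significant almost every time.

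Finally, regression to the mean should not be listed as a general reason for improvement. Selection is on MoCA, not on Schulte, and the entry window is bounded on both sides.

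**Conclusion.** The concern holds as an omission that permits misuse. The SAP gives within-arm before/after tests the same standing as between-arm tests, does not confine them to description, and expressly plans a between-arm test of change only for safety. Nothing prevents outcome 1 from being answered by a paired test in the Mexidol arm.

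With no drug effect, that test would be significant in 18.5% of trials at d=0.2 and 99% at d=0.8. The discordant pattern would occur in 1–25% of trials per outcome for d between 0.1 and 0.8, against 2.5% false favourable results from a between-arm test. These figures depend on the assumed d, 30 per arm and two-sided testing. The qualitative point needs only recovery, rehabilitation and repeat testing in both arms, all of which the protocol describes. The plan should be corrected, but the randomised comparison itself is intact.

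**What to change.** In the SAP paragraph on quantitative comparisons, state that within-arm before/after results are descriptive only. State also that every efficacy conclusion, including outcome 1, rests on the between-arm difference at a named visit, adjusted for the baseline value already collected (ANCOVA or a mixed model) and reported as an estimate with a 95% CI. In the protocol, clarify outcome 1 as the difference from standard therapy in Schulte change.

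No new data are needed. The cost is a dated SAP amendment plus the matching protocol clarification. Because enrolment is already recorded as actual, that clarification must be documented as made after enrolment. There will also be fewer significant results to report. With 30 per arm, an unadjusted between-arm comparison of change has about 49% power at a standardised difference of 0.5 and about 80% at 0.73 (normal approximation), so the confidence interval will matter more than the p-value.

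### Ischemic stroke and traumatic brain injury are pooled with no stated onset window or stratification factor, and the between-arm efficacy tests use neither diagnosis nor time since onset: precision is lost and chance imbalance goes uncorrected

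*Combined protocol and SAP*

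**What the plan says.** The Conditions row and the Inclusion Criteria of the Study Protocol define the population as "Acute Cerebral Failure (Ischemic Stroke, Traumatic Brain Injury"). The criterion that narrows the cognitive deficit is "Montreal Cognitive Assessment (MoCA test) >15; ≤22". No inclusion or exclusion criterion gives a time from event to Day 1; the only temporal restriction is the undefined word *acute*.

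The Study Design row gives "Allocation: Randomized (1:1") and "Enrollment: 60 [Actual"]. No method of allocation, block size or stratification factor is named.

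For efficacy, the Statistical Analysis Plan says "Comparison of groups by quantitative indicators can be carried out using the Student's T-test and the Mann-Whitney test". Dichotomous outcomes are compared by chi-square or Fisher tests, and results are tabulated by visit and arm. Diagnosis and time since onset do not appear as a stratum, covariate, subgroup or interaction. The only stratification the SAP mentions concerns adverse events, by severity and frequency. Repeated-measures ANOVA is reserved for quantitative safety parameters and also has no diagnosis term.

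**The concern.** The outcomes are changes on cognitive, mood and functional scales over 66 days, when patients also recover spontaneously. Diagnosis and time since the event are natural prognostic factors for that recovery. The MoCA window restricts the starting score, not the slope: two patients who both score 20 may be recovering at different rates.

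Two things are at stake. Leaving diagnosis out of the comparison puts the between-diagnosis difference into the error term, which widens the intervals. And in a trial of 60, the diagnosis mix can differ noticeably between arms by chance. When it does, the estimate moves by a corresponding amount, toward or away from Mexidol, and nothing in the SAP takes that out. The secondary purpose of separating responders from non-responders is exposed too, because a faster-recovering diagnosis could look like drug response.

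**Working it through.** **Inputs from the documents.** N = 60 and 1:1 allocation (Study Design), taken as 30 per arm; significance level from "Statistically significant values are p-level <0.05", taken as two-sided because sidedness is not stated. The documents give no power, SD or effect size, so there is no stated figure to reproduce.

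**Assumed inputs, not in the documents.** K = 20 to 30 TBI patients among the 60; a gap D in mean natural recovery between diagnoses of 0.5 to 1 within-diagnosis SD.

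**1. Chance imbalance.** With no stratification, the number x of TBI patients in one arm is hypergeometric (60 patients, K with TBI, 30 drawn). The difference in TBI share between arms is (2x − K)/30.

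| | K = 20 | K = 30 |
|---|---|---|
| Difference of 20 points or more, either direction | 17.0% | 19.6% |
| Difference of 20 points or more, favouring Mexidol | 8.5% | 9.8% |
| Difference of 13.3 points or more, either direction | 41.2% | 43.9% |

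**2. Shift in the estimate.** Shift = difference in share × D. At 20 points: 0.20 × 0.5 = 0.10 SD, and 0.20 × 1 = 0.20 SD.

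**3. Conditional false-positive rate.** Given a 20-point imbalance favouring Mexidol and no drug effect, the normal approximation is P(Z > (1.96 × SE_test − shift)/SE_true). SE_true = √(2/30) = 0.258. SE_test = √(2v/30), where v = 1 + 0.24 × D² at an even overall split (shares of 60% and 40%).
- D = 0.5: v = 1.06, SE_test = 0.266; (0.521 − 0.10)/0.258 = 1.63, giving about 5%.
- D = 1: v = 1.24, SE_test = 0.288; (0.564 − 0.20)/0.258 = 1.41, giving about 8%.

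The nominal value in that direction is 2.5%.

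**4. Overall false-positive rate.** Averaging the same expression over the whole hypergeometric distribution gives 2.5% in the direction of Mexidol for every combination of K and D. Perfectly balanced allocations have about 1.4-2.2%, which offsets the unfavourable ones. In simulation (40,000 trials per scenario) the two-sided error of the unadjusted t-test was 0.050 to 0.052.

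**5. Precision.** Ignoring diagnosis multiplies the outcome variance by 1 + p(1 − p)D². At p = 0.5 this is 1 + 0.25 × 0.25 = 1.06 for D = 0.5 and 1 + 0.25 × 1 = 1.25 for D = 1.

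Simulated power for a true effect of 0.72 SD, about the effect that 30 per arm detects with 80% power when there is no gap:

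| K | D | Unadjusted | Adjusted for diagnosis | Loss (points) |
|---|---|---|---|---|
| 20 | 0.5 | 0.761 | 0.776 | 1.5 |
| 30 | 0.5 | 0.756 | 0.775 | 1.9 |
| 20 | 1.0 | 0.694 | 0.770 | 7.6 |
| 30 | 1.0 | 0.687 | 0.778 | 9.1 |

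Both columns use unstratified allocation. When the imbalance is 20 points or more against Mexidol, the unadjusted power falls to 60-61% (D = 0.5) or 37-39% (D = 1).

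**6. Time since onset.** It would act in the same way, but the documents give no distribution, so no figure can be attached to it.

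**The case against.** The strongest reply is that an unadjusted comparison of randomised arms is valid for the pooled population that the primary purpose names, and that adjustment buys efficiency rather than repairing a broken test. That stands, and it sets the limits of the point.

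A reader might infer from the 5-8% in step 3 that the trial's false-positive rate is inflated, or that stroke and TBI are systematically confounded with treatment. The documents do not support this: allocation is randomised, and step 4 shows the overall error stays nominal. Nor can the 17-20% be paired with the 5-8%. The first counts imbalance in both directions; the second applies only to imbalance favouring Mexidol, which is 8.5-10% of allocations.

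Two further inferences also go too far. The plan does not say that allocation was simple; its method is unspecified, and all that can be said is that no stratification is stated. Nor does the missing onset window show that patients actually entered at widely different times. The 10 days of intravenous treatment and the intensive rehabilitation schedule give some clinical context, though neither defines a window.

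It can also be said that the power loss is small unless the gap is near 1 SD. That is correct: at 0.5 SD it is under 2 points. What remains is that diagnosis is known for every patient at entry and costs almost nothing to include.

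**Conclusion.** The point holds as a matter of precision and of uncorrected chance imbalance. It does not show bias or an invalid test. With 20 to 30 TBI patients, one allocation in five or six has a TBI-share difference of at least 20 points; half of these favour Mexidol. With a recovery gap of 0.5 to 1 SD, a 20-point difference moves the estimate by 0.1 to 0.2 SD, and ignoring diagnosis costs about 2 to 9 points of power for a 0.72 SD effect.

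That the plan omits diagnosis and onset time is certain from the text. The sizes rest on assumptions about the diagnosis mix, the recovery gap, 30 patients per arm and two-sided testing. The contribution of onset time is unquantified.

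**What to change.** In the SAP, replace the unadjusted between-arm comparisons of the clinical scales with a linear model containing arm, diagnosis (ischemic stroke or TBI) and, where the event date was recorded, days from event to Day 1. For non-normal indicators, use a van Elteren test stratified by diagnosis. That test leaves onset time unadjusted, so where onset is available a rank-based ANCOVA or a proportional-odds model with both covariates is the fuller choice; name one in advance. Show the arm difference within each diagnosis descriptively.

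Stratified allocation by diagnosis would be relevant only if randomisation were not already complete, and enrolment is listed as actual. Adjustment alone recovers most of the loss: 0.77 to 0.78 power in simulation, against 0.69 to 0.76 unadjusted.

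The cost is SAP wording and one or two degrees of freedom out of 60 patients. Diagnosis is known from the entry criterion. That the event date was captured is only an inference from the anamnesis row in Table 1, whose content is not described; if it was not captured, the onset term needs retrieval from source records or must be dropped, and the diagnosis adjustment still stands.
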